#### **4.2 Gender-Based Risks**

A TAVR literature and background information search, pertaining to sex or gender differences in the intended patient population, did not reveal either a gender disparity favoring one gender over the other, or a race or ethnic disparity. This review shows that in over 50 studies, the median female percentage is 52% with a maximum of 94% female participation. It is however evidenced in the literature that the risks experienced in TAVR can be observed in a higher rate within the female groups. The CoreValve ADVANCE study revealed that females experienced a higher rate of stroke, major vascular complications, and major bleeding. Similarly, Buchanan et al. (2011) concluded that female sex was a predictor of major vascular complications with females requiring more transfusion. No differences were noted amongst patients undergoing TAVI in composite safety and efficacy endpoints according to sex. Female subjects, however, had a better 1 year survival rate in the Sapien PARTNER trial. Also, Humphries et al. (2012) in a study of 641 consecutive patients (51.3% female) showed that female gender is associated with better short- and long-term survival after TAVR. This is also evidenced in the PARTNER 1A findings.

[REDACTED]

[REDACTED]

[REDACTED]

#### **4.4 Benefits**

There are no guaranteed benefits from participation in this study. Implantation of the transcatheter heart valve in the annular position may result in one or more of the following: improved valvular function, acute alleviation of symptoms related to aortic stenosis, improved morbidity and mortality.

Additionally, information gained from the conduct of this study may be of benefit to other people with the same medical condition in the future. The long-term results of using the study valve are not known at the present time. Alternative treatments include palliative medical therapy, aortic balloon valvuloplasty, transcatheter aortic valve delivery and surgical replacement of the aortic valve.

#### **5 Study Population (Pivotal IDE and CAP)**

The PORTICO clinical study is limited to two subject cohorts with severe, symptomatic aortic stenosis who are determined to be at high or extreme operative risk for surgical aortic valve replacement. The operative risk determination of study candidates will be based on the Society of Thoracic Surgeons (STS) Adult Cardiac Surgery Risk Calculator. Subject case review

[REDACTED]

will be conducted by the Subject Selection Committee to determine the patient's eligibility to receive Portico valve.

These subject cohorts are defined as follows:

**High risk cohort:**

The **high risk** cohort is defined as subjects with severe aortic stenosis symptoms for whom conventional aortic valve replacement surgery is associated with high risk equivalent to an STS risk score that is  $\geq 8\%$ .

**Extreme risk cohort:**

The **extreme risk** cohort is defined as subjects with severe aortic stenosis symptoms and deemed unsuitable for conventional aortic valve replacement because of predicted probability of  $\geq 50\%$  mortality, or at risk for a serious irreversible complication by 30 days.

The surgical risk of study candidates will be determined by the heart team's interventional cardiologist(s) and cardiac surgeon(s) assessments taking into consideration the STS Adult Cardiac Surgery Risk Calculator.

**5.1 Inclusion Criteria**

**High Risk Cohort:**

All candidates for the High Risk Cohort of this study must meet **all** the following inclusion criteria:

1. Subjects must have co-morbidities such that the surgeon and cardiologist Co-Investigators concur that the predicted risk of operative mortality is  $\geq 15\%$  or a minimum STS score of 8%. A candidate who does not meet the STS score criteria of  $\geq 8\%$  can be included in the study if a peer review by at least two surgeons concludes and documents that the patient's predicted risk of operative mortality is  $\geq 15\%$ . The surgeon's assessment of operative comorbidities not captured by the STS score must be documented in the study case report form as well as in the patient medical record.
2. Subject is 21 years of age or older at the time of consent.
3. Subject has senile degenerative aortic valve stenosis with echocardiographically derived criteria: mean gradient  $> 40$  mmHg or jet velocity greater than 4.0 m/s or Doppler Velocity Index  $< 0.25$  and an initial aortic valve area (AVA) of  $\leq 1.0$  cm^2

(indexed EOA  $\leq 0.6 \text{ cm}^2/\text{m}^2$ ). (Qualifying AVA baseline measurement must be within 60 days prior to informed consent).

4. Subject has symptomatic aortic stenosis as demonstrated by NYHA Functional Classification of II, III, or IV.
5. The subject has been informed of the nature of the study, agrees to its provisions and has provided written informed consent as approved by the Institutional Review Board (IRB) of the respective clinical site.
6. The subject and the treating physician agree that the subject will return for all required post-procedure follow-up visits.
7. Subject's aortic annulus is 19-27mm diameter as measured by CT conducted within 12 months prior to informed consent. Note: if CT is contraindicated and/or not possible to be obtained for certain subjects, a 3D echo and non-contrast CT of chest and abdomen/pelvis may be accepted if approved by the subject selection committee.

#### **Extreme Risk Cohort:**

All candidates for the Extreme Risk Cohort of this study must meet # 2, 3, 4, 5, 6, 7 of the above criteria, **and**

1. The subject, after formal consults by a cardiologist and two cardiovascular surgeons agree that medical factors preclude operation, based on a conclusion that the probability of death or serious, irreversible morbidity exceeds the probability of meaningful improvement. Specifically, the probability of death or serious, irreversible morbidity should exceed 50%. The surgeons' consult notes shall specify the medical or anatomic factors leading to that conclusion and include a printout of the calculation of the STS score to additionally identify the risks in these patients.

#### **All Candidates:**

Additionally, all candidates for the study must meet the following inclusion criteria for the TAVR Leaflet Motion Sub-study, until the minimum sub-study sample size has been achieved, as described in Appendix S. This sub-study is not applicable for subjects enrolled under protocol Version K or later (including CAP subjects) as the minimum sub-study sample size has been achieved:

Be willing and able to undergo, at both 30 days and 6 months post-implant, a Multi-Slice Computed Tomography (MSCT) scan (or TEE, if medically or technically contraindicated for a MSCT) of the heart and cardiac structures.

## 5.2 Exclusion Criteria

### High and Extreme Risk Cohort:

Candidates will be excluded from the study if **any** of the following conditions are present:

1. Evidence of an acute myocardial infarction (defined as: ST Segment Elevation as evidenced on 12 Lead ECG) within 30 days prior to index procedure.
2. Aortic valve is a congenital unicuspid or congenital bicuspid valve, or is non-calcified as verified by echocardiography.
3. Mixed aortic valve disease (aortic stenosis and aortic regurgitation with predominant aortic regurgitation 3-4+).
4. Any percutaneous coronary or peripheral interventional procedure performed within 30 days prior to index procedure.
5. Pre-existing prosthetic heart valve or other implant in any valve position, prosthetic ring, severe circumferential mitral annular calcification (MAC) which is continuous with calcium in the LVOT, severe (greater than 3+) mitral insufficiency, or severe mitral stenosis with pulmonary compromise. ***Subjects with pre-existing surgical bioprosthetic aortic heart valve should be considered for the Valve-in-Valve registry.***
6. Blood dyscrasias as defined: leukopenia (WBC<3000 mm^3), acute anemia (Hb < 9 g/dL), thrombocytopenia (platelet count <50,000 cells/mm^3).
7. History of bleeding diathesis or coagulopathy.
8. Cardiogenic shock manifested by low cardiac output, vasopressor dependence, or mechanical hemodynamic support.
9. Untreated clinically significant coronary artery disease requiring revascularization.
10. Hemodynamic instability requiring inotropic support or mechanical heart assistance.
11. Need for emergency surgery for any reason.
12. Hypertrophic cardiomyopathy with or without obstruction (HOCM).
13. Severe ventricular dysfunction with LVEF <20% as measured by resting echocardiogram.
14. Echocardiographic evidence of intracardiac mass, thrombus or vegetation.
15. Active peptic ulcer or upper GI bleeding within 3 months prior to index procedure.
16. A known hypersensitivity or contraindication to aspirin, heparin, ticlopidine (Ticlid), or clopidogrel (Plavix), or sensitivity to contrast media which cannot be adequately premedicated.
17. Recent (within 6 months prior to index procedure date) cerebrovascular accident (CVA) or a transient ischemic attack (TIA).

18. Renal insufficiency (creatinine > 3.0 mg/dL) and/or end stage renal disease requiring chronic dialysis.
19. Life expectancy < 12 months from the time of informed consent due to non-cardiac co-morbid conditions.
20. Significant aortic disease, including abdominal aortic or thoracic aneurysm defined as maximal luminal diameter 5cm or greater; marked tortuosity (hyperacute bend), aortic arch atheroma (especially if thick [ $> 5$  mm], protruding or ulcerated) or narrowing (especially with calcification and surface irregularities) of the abdominal or thoracic aorta, severe “unfolding” and tortuosity of the thoracic aorta (applicable for transfemoral patients only).
21. Native aortic annulus size < 19 mm or > 27 mm per the baseline diagnostic imaging.
22. Aortic root angulation > 70° (applicable for transfemoral patients only).
23. Currently participating in an investigational drug or device study.
24. Active bacterial endocarditis within 6 months prior to the index procedure.
25. Bulky calcified aortic valve leaflets in close proximity to coronary ostia.
26. Non-calcified aortic annulus
27. Iliofemoral vessel characteristics that would preclude safe placement of the introducer sheath such as severe obstructive calcification, or severe tortuosity (applicable for transfemoral patients only).

### 5.3 Screening Process

At the time the patient agrees to participate after receiving information and all the patient’s questions have been answered satisfactorily, the study informed consent form will be signed. Patients who sign an informed consent form and meet all the inclusion criteria and none of the exclusion criteria will be reviewed and confirmed by the Subject Selection Committee for participation eligibility. Subject selection should take place within 30 days from the date the subject provided informed consent. Once the subject is selected to participate in the study, baseline assessments and randomization (if applicable) can be completed. The index procedure should take place no later than 14 calendar days from subject enrollment.

Subjects who meet the subject selection criteria and are confirmed by the Subject Selection Committee will be assigned to cohorts based on their surgical risk level and either randomized into the pivotal IDE randomized cohort or enrolled into a study-defined registry (Roll-in or Valve-in-Valve), the FlexNav study or the CAP. Subjects who do not meet the selection criteria will not be scheduled for an implant procedure and will not be considered enrolled into the study.

If a subject is consented and undergoes study-specific testing (i.e., testing that would not be done if they were not being considered for the study) but is not enrolled in the study, the

subject should be followed for adverse events for 30 days from informed consent and then withdrawn from study participation.

For subjects consented under protocol version L or later, if a subject undergoes study-specific testing but does not undergo a Portico implant attempt with the FlexNav™ Delivery System the subject will not be considered enrolled in the study and will not require any further follow-up.

Figure 7 summarizes subjects' screening and enrollment flow.

Subject screening depends on the joint collaboration of investigators (including designated interventional cardiologist(s) and designated cardiac surgeon(s)) at each site. All suitable subjects must undergo the established institutional specific multidisciplinary team assessment to confirm both appropriateness for transcatheter aortic valve placement and high-risk designation. Both a cardiologist investigator and a cardiac surgeon investigator must be involved in the subject selection and screening process. All subjects evaluated for severe aortic stenosis in medical and surgical departments that are high or extreme risk candidates for AVR should be screened for study eligibility.

The investigators are responsible for ensuring subject eligibility. Study sites will maintain a log of all the screened subjects and subjects enrolled. Reasons for meeting study criteria but failing to be enrolled will be captured on the screening log and may be monitored by SJM.

### **5.3.1 Additional Exclusion Criteria (Transcatheter Access-Related)**

For subjects who do not qualify for transfemoral access, the following exclusion criteria will be used to screen for an appropriate alternative access delivery method.

#### **5.3.1.1 Transaortic Subject Cohort Specific Exclusion Criteria**

1. Subject has pre-existing patent RIMA graft that would preclude access.
2. Subject has a hostile chest or other condition that complicates transaortic access.
3. Subject has a porcelain aorta, defined as an extensive circumferential calcification of the ascending aorta that would complicate TAO access.

For subjects enrolled under version L of the protocol, the following exclusion criteria apply for transaortic access using the FlexNav™ Delivery System:

1. Subject has a distance between the annular plane and the aortic access site <7 cm (2.8")
2. Subject has a distance between the annular plane and the separate introducer sheath distal tip <6 cm (2.4")

#### **5.3.1.2 Subclavian/Axillary Subject Cohort Specific Exclusion Criteria**

1. Subject's access vessel (subclavian/axillary) diameter will not allow for introduction of the applicable 18 Fr or 19 Fr delivery system.
2. Subject's subclavian/axillary arteries have severe calcification and/or tortuosity.

3. Subject's aortic root angulation is:
  - Left Subclavian/Left Axillary: >70°
  - Right Subclavian/Right Axillary: >30°

4. Subject has a history of patent LIMA/RIMA graft that would preclude access

For subjects enrolled under version L of the protocol, the following exclusion criteria apply for subclavian/axillary access using the FlexNav™ Delivery System:

1. Subject's access vessel (subclavian/axillary) has a distance between the annular plane and the integrated sheath distal tip <17 cm (6.7")
2. Subject's access vessel requires the delivery system to be advanced through a separate introducer sheath

For selection of the appropriate alternative access method, subjects will be screened using the access specific exclusion criteria, and the selection of the alternative access method will be based on the evaluation by the site and the Subject Selection Committee.

[figure not shown]

[figure not shown]
Figure 7: Study Conduct Flowchart (Pivotal IDE and CAP)

## 6 Subject Assignments

Subjects will be assigned to one of the following cohorts:

### 6.1 High Risk Cohort (Pivotal IDE)

High risk subjects with an annular size between 19-27mm who qualify for transfemoral access and have a suitable iliofemoral vasculature for both Portico valve and an FDA approved commercially available transcatheter valve (CAV) will be randomized into the transfemoral arm to receive either the Portico valve or the CAV. Subjects who do not qualify for the transfemoral access arm (iliofemoral vasculature is not suitable for both Portico and CAV) will be randomized within the alternative access arm to receive either the Portico valve or CAV (Figure 8 ).

[figure not shown]
TF=Transfemoral, CAV= Commercially Available Transcatheter Valve, AA=Alternative Access

Figure 8. High Risk Cohort Flow Chart

### 6.2 Extreme Risk Cohort (Pivotal IDE)

Extreme risk subjects will be assigned to the Extreme Risk Cohort as follows:

Extreme risk subjects with annular size between 19-27mm who qualify for transfemoral access and have suitable iliofemoral vasculature suitable for both Portico and CAV will be randomized into the transfemoral arm to receive either the Portico valve or CAV. Subjects who do not qualify for the transfemoral access arm (iliofemoral vasculature is not suitable for both Portico and CAV) will be randomized within the alternative access arm to receive either the Portico valve or CAV (Figure 9 ).

TF=Transfemoral, CAV= Commercially Available Transcatheter Valve, AA=Alternative Access

**Figure 9. Extreme Risk Cohort Flow Chart**

### 6.3 Valve-in-Valve Registry

Subjects who have documented failed aortic surgical valve prosthesis and are deemed eligible to receive a transcatheter Portico valve into the existing bioprosthesis will be considered for eligibility in the Valve-in-Valve registry. The Valve-in-Valve registry will enroll up to 100 qualified subjects from the pivotal IDE trial or CAP.

Valve-in-valve registry subjects must meet all the applicable inclusion criteria and none of the applicable exclusion criteria for the high or extreme risk cohort (Sections 5.1 & 5.2).

Examples of criteria that may not apply include inclusion criterion numbers **3** and **4** (the bioprosthetic valve may be stenotic or require replacement due to other forms of structural valve deterioration), and exclusion criterion numbers **2**, **3**, **5** (existing surgical bioprosthetic aortic valve), **21**, and **26**. If the subject has a bioprosthetic valve in another location, the subjects will be excluded from the PORTICO clinical study.

Valve-in-valve subjects' data will not be included in the randomized population nor the primary data analysis; however, the data will be analyzed and presented separately to support an expanded indication for Valve-in-Valve use (Portico-in-SAVR).

All Valve-in-Valve subjects enrolled under protocol version L or later will have a Portico valve implanted using the FlexNav™ Delivery System. Implanting physicians will be required to have completed a minimum of one (1) roll-in subject in the FlexNav study before enrolling a subject in the IDE Valve-in-Valve registry.

### 6.4 Roll-in Registry

Prior to enrolling subjects in the pivotal IDE randomized cohort, sites will be required to complete a minimum of two (2) and up to three (3) roll-in patients per primary implanting physician. However, implanting physicians with prior Portico experience and with a minimum of 3 implants in the last 6 months will not be required to include roll-in patients.

For subjects enrolled under protocol version L or later, all primary implanting physicians irrespective of prior Portico implant experience will be required to complete a minimum of one (1) and up to three (3) roll-in patients using the FlexNav™ Delivery System.

All roll-in subjects will be added to the IDE Roll-in Registry. The roll-in subjects must meet all the inclusion criteria and none of the exclusion criteria and be approved by the Subject Selection Committee. These subjects will be followed per protocol for the duration of the study, or until subject's withdrawal or death. The roll-in subjects' data will not be included in the randomized population nor the primary data analysis; however, the data will be analyzed and presented separately.

### **6.5 FlexNav Study**

High and extreme risk subjects with an annular size between 19-27mm with suitable anatomy for transfemoral or alternative access valve implantation using the FlexNav™ Delivery System (minimum vessel requirement  $\geq 5\text{mm}$ ) will be enrolled in the FlexNav study. All FlexNav study subjects will receive a Portico device (no randomization).

The number of roll-in patients required by a site before they can contribute to the FlexNav study will be at the discretion of the Sponsor. All roll-in subjects will be designated as such prior to enrollment and will be added to the IDE Roll-in Registry.

Following the successful completion of roll-in subjects, sites will enroll subjects into the FlexNav study. These enrolled subjects will be considered part of the 'analysis population'.

Analysis subject data (excluding roll-ins) will be summarized and presented separately to the randomized cohort in the PMA application.

### **6.6 Continued Access Protocol (CAP)**

After the pivotal IDE trial has met its minimum sample-size for the randomized cohort and the FlexNav study, sites may choose to participate in the CAP and enroll high and extreme risk subjects with an annular size between 19-27mm with suitable anatomy for transfemoral or alternative access valve implantation. All CAP subjects will receive a Portico valve (no randomization).

### **6.7 Screening**

Data available in the patient's medical record may be utilized to fulfill screening and baseline requirements and testing does not need to be repeated if performed within 60 days prior to informed consent. Computed Tomography (CT) scan with angiography and coronary and aortic angiogram (with runoff if clinically indicated) may be performed within 12 months prior to informed consent.

After subject informed consent is obtained, study-specific screening evaluation may be conducted to determine inclusion in the study. All cardiac medications and all medications given for cardiovascular effect may be continued at their prescribed dosages.

1. Demographics
2. Medical History
3. Canadian Cardiovascular Society (CCS) Angina Scale Assessment
4. Surgical Risk Assessment tools (STS Risk Score, and EuroSCORE II)
5. Forced Expiratory Volume (FEV1), if clinically indicated
6. Physical Exam
7. Echocardiography to include comprehensive transthoracic or transesophageal 2D echocardiogram, including assessment of aortic valve gradients (mean and peak), areas, indices, degree of regurgitation, cardiac output and cardiac index, left ventricle systolic function (global and segmental)
8. Lab Measurements (per Table 9, Table of Assessments)
9. 12 Lead Electrocardiogram (ECG)
10. Computed Tomography Scan with Angiography for chest, abdomen and pelvis: aortic root and valve annulus sizing, assessment of suitability of iliofemoral access, and determination of appropriate coaxial angles for optimizing the valve implantation procedure. CT scan performed up to 12 months prior to consent will be acceptable.
11. 3D Transesophageal Echocardiogram (TEE) if CT is contraindicated
12. New York Heart Association (NYHA) Functional Classification
13. Frailty Index Assessment
  - a. Katz Index of Activities of Daily Living
  - b. Grip strength
  - c. 15 ft. walk
14. Coronary and aortic angiogram (arteriograms of the lower abdominal aorta to the femoral arteries), with runoff if clinically indicated. Coronary and aortic angio performed up to 12 months prior to consent will be acceptable.

## **6.8 Baseline Assessments**

The following baseline data will be collected for all subjects prior to the index procedure.

1. Chest X-ray
2. Cardiovascular medications documentation
3. Modified Rankin Scale (mRS)
4. NIH Stroke Scale (NIHSS)
5. Barthel Index
6. Quality of Life Measures (QoL) (For CAP subjects enrolled under Ver. K or later, only the KCCQ and EQ-5D are required.)

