7. MMSE-2:SV
8. Six Minute Walk Test (6MWT) (Not required for CAP subjects enrolled under Ver. K or later)

9. Troponin or CK/CK-MB, INR (if subject is on Coumadin or Warfarin)

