## 6.9 Subject Enrollment and Randomization

All subjects who meet the study eligibility requirements will be assigned into an applicable registry (Roll-in or Valve-in-Valve), the FlexNav study, the CAP or one of the pivotal IDE randomized cohorts for operability, followed by delivery method determination based on vascular access (Figure 10).

Subjects will be considered enrolled into the study after completion of all of the following steps:

1. Signed informed consent is obtained.
2. Based on the screening assessments, it is determined that the subject meets all of the inclusion and none of the exclusion criteria.
3. Subject is approved by the subject selection committee.
4. The trial cohort has been determined, and understood by the subject.
5. The subject is randomized (pivotal IDE only) or assigned to the appropriate registry or CAP.

In the FlexNav study and the CAP (under protocol version L), the subject will be considered enrolled once steps 1-4 above are complete and when the FlexNav™ Delivery System enters the subjects' body.

[figure not shown]
For the pivotal randomized IDE cohort, the subject will be randomized based on the cohort assignment as follows:

- The high risk cohort will be randomized against an FDA-approved and commercially-available transcatheter valve on a 1:1 basis.
- The extreme risk cohort will be randomized against an FDA-approved and commercially-available transcatheter valve on a 1:1 basis.

It is strongly recommended the implant procedure take place no later than 14 calendar days from subject enrollment/randomization

Once a subject is randomized in the pivotal IDE, crossover from one arm to the other is not allowed. However, following randomization or enrollment in the FlexNav Study, registry or the CAP, those subjects who are scheduled to receive a transcatheter valve via transfemoral access and found not to be suitable for this delivery modality (per the heart team medical decision) can receive a transcatheter valve using an alternate access modality and vice versa. However, this will be considered a protocol deviation unless multiple access routes were pre-approved by the Subject Selection Committee. The rationale for this decision must be documented.

In the pivotal IDE trial, when subjects are randomized to receive a CAV, the subject selection and procedure must follow the FDA-approved instructions for use (IFU).

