### **7.3 Index Procedure**

The heart team's interventional cardiologist(s) and cardiac surgeon(s) must jointly participate in the intra-operative technical aspects of TAVR.

The index procedure should occur within 14 calendar days following subject randomization, registry or CAP assignment. The procedure must be performed according to the instructions for use (IFU) for the assigned device. Antiplatelet/Anticoagulation and other medications should be administered per the standard of care.

Cardiac enzymes must be obtained prior to the index procedure and within approximately 72 hours after the procedure.

Cardiac rhythm should be monitored and recorded at the following time points:

1. Upon crossing native valve with the guidewire
2. Upon positioning of the guidewire
3. Prior to valvuloplasty (if performed)
4. Immediately post valvuloplasty (if performed)
5. Before valve crosses the AV valve
6. After valve crosses the annulus
7. After valve is deployed in final position

The following data should be collected pre and post implant:

1. Aortic systolic/diastolic pressure, Mean aortic pressure, Mean AV gradient, Peak AV gradient
2. Simultaneous Aortic and LV pressure measurements for valve area calculation
3. A supra-aortic angiogram for valve performance and coronary patency
4. Device deployment information
5. If performed, right atrial (RA) pressure, pulmonary artery (PA) systolic/diastolic pressure, Mean PA pressure, pulmonary wedge pressure (PCWP)

The activated clotting time (ACT) should be monitored and recorded on source documentation during the procedure and adjusted to attempt to keep the subject's ACT > 250 seconds.

If an enrolled subject is not implanted with a TAVR valve, the following will apply:

- Randomized subjects will be followed per protocol through the one-year visit, as part of the primary analysis intent to treat (ITT) population, and then terminated from the study.
- Registry-assigned (Roll-in or Valve-in-Valve), FlexNav study and CAP subjects will be assessed for any adverse events through 30 days post procedure, and then terminated from the study.

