1.6 Blinding

Subjects were not blinded to their assigned treatment. Packaging and design of the Portico and CAVs are different, and thus, implanters were not blinded to the assigned treatment. There was no randomization or blinding of treatment in the FlexNav cohort.

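### Does the plan let baseline KCCQ, six-minute walk and mRS be recorded after patients know their assigned valve, and does that call for a change?

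*Protocol*

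**What the plan says.** Protocol 6.8 (Baseline Assessments) opens: "The following baseline data will be collected for all subjects prior to the index procedure". The list includes mRS, the quality-of-life instruments and, as item 8, "Six Minute Walk Test (6MWT) (Not required for CAP subjects enrolled under Ver. K or later"), so the walk applies to randomised patients.

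On sequence, Protocol 5.3 says: "Once the subject is selected to participate in the study, baseline assessments and randomization (if applicable) can be completed". Protocol 6.9 says: "Subjects will be considered enrolled into the study after completion of all of the following steps". The five steps are consent, eligibility from the screening assessments, committee approval, cohort determination, and randomisation or assignment. Completing the 6.8 list is not one of them.

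On the interval, Protocol 7.3 says: "The index procedure should occur within 14 calendar days following subject randomization, registry or CAP assignment". Protocol 6.9 words the same limit as a strong recommendation. On blinding, SAP 1.6 says: "Subjects were not blinded to their assigned treatment".

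Two other passages bear on timing. Protocol 5.1 ties the qualifying valve area to consent: "Qualifying AVA baseline measurement must be within 60 days prior to informed consent". Protocol 6.7 says that medical-record data "may be utilized to fulfill screening and baseline requirements and testing does not need to be repeated if performed within 60 days" before consent.

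**The concern.** In an open-label trial, a self-reported or effort-dependent baseline should be taken before the patient knows the allocation. A patient who is pleased or disappointed by the assigned valve may answer the KCCQ differently or walk a different distance. The baseline then carries a between-arm difference created by the allocation itself. Subtracting or adjusting for it moves that difference into the treatment estimate.

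The visible rules leave room for this. The only stated limit is the procedure, randomisation can come up to two weeks earlier, and the enrolment steps do not require baseline to be complete. KCCQ, six-minute walk and mRS are also absent from the 6.7 screening list, so the eligibility step does not bring them forward.

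KCCQ and six-minute walk are tested secondary non-inferiority endpoints (Protocol 11.5) within the multiplicity scheme (SAP 2.11). Disabling stroke, a component of both primary endpoints, is defined in Appendix C partly by a rise from the pre-stroke mRS.

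**Working it through.** The plan gives no figure on this point to reproduce. The check is mainly a reading of the passages, followed by a conditional calculation of what a late baseline could do.

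**1. Does any visible sentence require baseline before randomisation?** No. Protocol 5.3 names baseline first but joins the two with a plain conjunction; 6.8 names only the procedure; 6.9 is silent. The literal reading is correct.

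**2. Does the wording of 6.8 show that post-allocation collection was intended?** No.
- It covers all subjects, including roll-in, valve-in-valve, FlexNav and CAP patients, who are never randomised. The procedure is the one anchor common to every cohort.
- Appendix J uses the same loose anchor for frailty. It places the assessment after consent and before the procedure, although its stated purpose is to judge risk before enrolment and 6.7 lists it as a screening item.
- The sections run screening (6.7), baseline (6.8), randomisation (6.9), and 5.3 names the last two in the same order.
- The valve-area rule in 5.1 is an eligibility criterion, so it has to precede enrolment. It says nothing about the order of other baseline measures.

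**3. Where would the order be set?** Protocol 7.13 refers the timeline to Table 9, and 5.3 refers the screening and enrolment flow to Figure 7; Figure 10 shows the study flow. None of these is reproduced in the public text. Section 11.2 and part of SAP 1.5 are redacted. Their absence cannot be counted as an omission from the plan.

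**4. Which analyses use these baselines?**
- KCCQ and six-minute walk tests: worded as one-year endpoints, with the models redacted.
- Descriptive item 15, quality of life from baseline: the only visible KCCQ, quality-of-life or walk endpoint in the randomised cohort that uses baseline.
- mRS: the reference is the pre-stroke value. It is repeated at discharge, 30 days, 6 months, one year and annually, scored by a certified rater, neurologist or neurology fellow (Table 10), and strokes are adjudicated (10.1). The study baseline matters mainly for strokes close to the procedure.

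**5. Size, conditional on assumptions.** Let p be the share of baselines taken after allocation is known (taken as equal in the two arms), s the between-arm shift in those baselines, and w the weight the analysis gives to baseline. In absolute value:

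bias = p × s × w, with w = 1 for change from baseline, w = slope for ANCOVA, and w = 0 for the one-year value alone.

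The documents give neither p nor s. Assume s = 2 KCCQ points, p = 0.1 to 1 and slope = 0.3 to 0.5:

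| Analysis | Low | High |
|---|---|---|
| Change from baseline | 0.1 × 2 × 1 = 0.2 | 1 × 2 × 1 = 2.0 |
| ANCOVA | 0.1 × 2 × 0.3 = 0.06 | 1 × 2 × 0.5 = 1.0 |
| One-year value alone | 0 | 0 |

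If the late share differs by arm, p × s becomes p₁s₁ − p₂s₂. Nothing comparable can be given for the walk test.

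**6. Cost of avoiding baseline altogether.** With r the baseline to one-year correlation (assumed 0.3 to 0.5) and equal variances, the standard error of the one-year analysis relative to:
- ANCOVA is 1/√(1 − r²): 1/√0.91 = 1.048 at r = 0.3 and 1/√0.75 = 1.155 at r = 0.5, so the interval is about 5% to 15% wider;
- a change score is 1/√(2(1 − r)): 1/√1.4 = 0.845 at r = 0.3 and 1/√1.0 = 1.00 at r = 0.5, so the interval is about 15% narrower or unchanged.

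Whether dropping baseline costs precision therefore depends on a model that is redacted.

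**7. Whom would new wording reach?** Protocol 1.2.1 has every active arm using FlexNav from version L onward. Appendix W 10.3 describes the randomised Portico arm as the first-generation system, and SAP 1.6 reports blinding in the past tense. Randomised accrual looks complete or nearly so.

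**The case for a change.** The best argument for acting is that the remedy is almost free: one line each in 6.8 and 6.9, with no added visit or test. The affected measures are not trivial, since one-year KCCQ is a tested endpoint and is also listed for the Medicare coverage decision. The 60-day record provision in 6.7 is a permission and does not close the window, and the 14-day limit is itself only advisory. If the redacted KCCQ model uses baseline, the test would be exposed.

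Part of this stands. The visible text does not forbid a post-allocation baseline, and a sponsor asked about it should be able to point to Table 9 or Figure 7. The rest is conditional: it needs those exhibits to be silent, sites to depart from the usual order, the shift to differ between two arms that both receive a transcatheter valve, and the redacted models to use baseline. None of these can be shown from the documents. The inexpensive wording would also probably reach few or no randomised patients.

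**Conclusion.** The literal observation is right, but it does not call for a change to the plan. The visible sequence suggests baseline before randomisation, the procedure is a sensible common anchor for cohorts with no randomisation, and the exhibits that would state the order are outside the public text. No hypothesis test is shown to be affected: bias is zero for a one-year value tested alone, and the one visible from-baseline quality-of-life summary is descriptive. The 0.2 to 2.0 point (change score) and 0.06 to 1.0 point (ANCOVA) ranges rest entirely on an assumed 2-point shift, an assumed late share of 10% to 100% and an assumed slope of 0.3 to 0.5. They do not estimate what happened in this trial, and neither size nor direction is known.

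At most this is a query to the sponsor. Analysts can handle it from assessment and randomisation dates by counting, by arm, the baselines dated after randomisation. If that count were material and a redacted test did use baseline, an ITT analysis of the one-year value would be a natural sensitivity check, with the precision trade-off shown above.
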